### **8.8. Study Size**

The sample size for this study is fixed by the duration of the observation window. No formal sample size computation was performed. All patients who meet inclusion/exclusion criteria will be included in the analyses.

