## Secondary Objectives

- **Explore the differences in demographic and clinical characteristics among tofacitinb+MTX patients who discontinue MTX vs. persist with MTX or experience interrupted MTX.**

For this objective descriptive analysis will be conducted. The goal of this objective will be to describe the respective populations and explore the presence of demographic differences between the cohorts. Known demographic characteristics (eg, age, gender geographic location, pre-index cost and utilization) will be summarized. In addition, other patient characteristics (eg, most common comorbid diagnoses and most common medications received) will be summarized.

- **To compare RA-related costs among tofacitinb+MTX patients who discontinue MTX vs. persist with MTX or experience interrupted MTX.**

For this objective both descriptive and multivariable analysis will be conducted. For the descriptive analysis, 12-month RA-related cost measures will be presented per patient during the baseline and follow-up periods. The change in health care cost from baseline to follow-up will be identified. In addition, total RA-related health care cost will be presented in each of the months of the baseline and follow-up. The mean cost in each month will be included on a figure demonstrating the trend in costs over time. Multivariable analysis of cost will also be conducted using generalized linear models (see [Section 8.10.3](#)).

- **Compare medication effectiveness using a validated claims-based algorithm among tofacitinb+MTX patients who discontinue MTX vs. persist with MTX or experience interrupted MTX.**

Medication effectiveness at one year will be examined by the medication cohorts of interest using patients who have at least 1 year of follow-up. For this objective both descriptive analysis and multivariable analysis will be used. Descriptive analysis will focus on quantifying the percentage of patients who are effectively treated at one year. Analysis of this objective may also include multivariable analysis (eg, logistic regression). Specifically, the dependent variable will be effectively treated at one year (yes/no) and the independent variables will be study cohort, demographic characteristics, characteristics of interest, and other characteristics identified from previous objectives (see [Section 8.10.4](#)).

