#### **8.10.2. Multivariate Analysis**

To control for possible confounding of the relationship between the outcomes and independent variable of interest, select objectives will be conducted utilizing multivariable methods as described above.

Final outcomes for multivariate analysis will be selected after review of descriptive results. Possible outcomes of interest include: total all-cause health care cost, total RA-related health care cost, cost of biologics/tofacitinib/administration/nb-DMARDs, medication effectiveness (yes vs. no).

For each model, specific predictors to be included will be determined based upon clinical rationale and statistical significance. Variables listed in [Section 8.6.1](#) and [8.6.2](#) will be considered for inclusion in the multivariable models. Additional variables identified throughout the course of the study will also be considered. Following standard procedure,

regression diagnostics will be performed for each model to assess goodness of fit and violations of model assumptions (eg, multicollinearity, heteroskedasticity). When there are violations of the model, programmers will note them and make appropriate corrections to the data (ie, typically through transformation of either the independent or dependent variables) or in the method of estimation.

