### **8.10.6. Decomposition**

Given that the sample size for this study will be relatively small and the comparator populations will be noticeably different, implementing propensity score matching may reduce the available sample below what is needed for a meaningful study. One possible solution would be to implement a method known as decomposition [Blinder (1973), Oaxaca (1973)] Decomposition splits out the treatment effect into two parts, the effect of the actual treatment and the effect of the other differences between the treatment groups. Presumably, if the treatment groups were randomly assigned, then the effect of the treatment would be the entire effect and the effect of all other differences would be negligible. However, since biologic treatment choice is not randomly assigned, the decomposition method would determine how much of the treatment effect is due to the medication and how much is due to the difference in characteristics between the two tofacitinib cohorts (tofacitinib+MTX patients who withdraw MTX or continue MTX).

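### Section 8.10.2 lets statistical significance help choose confounders and protects none of them, so real confounders can be dropped in a study expected to be small and imbalanced

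*Combined protocol and SAP*

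**What the plan says.** Section 8.10.2 gives the purpose of the models: "To control for possible confounding of the relationship between the outcomes and independent variable of interest". On covariates it says: "For each model, specific predictors to be included will be determined based upon clinical rationale and statistical significance". The variables of 8.6.1 and 8.6.2 are not required; they "will be considered for inclusion in the multivariable models". The pool is also open: "Additional variables identified throughout the course of the study will also be considered".

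For the effectiveness model, section 8.10 (Secondary Objectives) lists cohort and demographics as independent variables. It then adds an undefined group of characteristics of interest, and "other characteristics identified from previous objectives".

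On size and balance, 8.10.6 expects that "the sample size for this study will be relatively small and the comparator populations will be noticeably different", and 8.8 states: "No formal sample size computation was performed". Sections 8.10.3 to 8.10.5 report ordinary 95% intervals and p-values, with no allowance for covariate selection.

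**The concern.** A covariate's p-value measures how clearly it predicts the outcome in this sample. It does not measure how much the covariate confounds the cohort comparison. A variable that differs strongly between cohorts and moderately affects the outcome can shift the cohort estimate appreciably and still have p>0.05 when N is small. A rule that uses significance can then remove it, although the model exists to control confounding.

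The candidate pool is wide. Three lists in 8.6.2 alone give 25 comorbid conditions + 25 medications + 11 comorbidity flags = 61 candidates. Section 8.6.2 also holds post-index measures (opioid, NSAID and corticosteroid use are captured after as well as before index), and 8.10.2 makes that section eligible without restriction. Adjusting for something measured after index can introduce bias of its own.

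At stake are the adjusted cohort effects on cost and on being effectively treated at one year. Both belong to secondary objectives. The primary treatment-pattern objective is planned as a summary and is not touched.

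**Working it through.** The plan gives no N, alpha, threshold or effect size, so there is no figure to reproduce. The check asks whether the mechanism operates and how strongly under stated assumptions. In every run the true cohort effect is zero, so the false-positive rate of the cohort term should be 5%, and interval coverage is 100% minus that rate.

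**Step 1: chance that a true confounder survives p<0.05.** Assume an outcome effect of b = 0.12 SD per SD. Approximate chance = Φ(b√N − 1.96).
- N=150: Φ(1.47 − 1.96) = Φ(−0.49) = 31%
- N=300: Φ(2.08 − 1.96) = Φ(0.12) = 55%
- N=600: Φ(2.94 − 1.96) = Φ(0.98) = 84%

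**Step 2: bias at stake.** Assume 8 independent confounders, each differing by 0.4 SD between cohorts. With no adjustment the bias is 8 × 0.12 × 0.4 = 0.384 SD (simulated: 0.384 to 0.388). After backward elimination at 0.05, the simulated remaining bias is 0.176 SD at N=150, 0.112 at N=300 and 0.036 at N=600. With all eight forced in it is at most 0.005.

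**Step 3: false-positive rate, confounders only.** Linear outcome, cohorts 40%/60%, 3,000 replicates, backward elimination at 0.05:

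| Imbalance per confounder | N=150 | N=300 | N=600 | N=1000 |
|---|---|---|---|---|
| 0.2 SD | 10.6% | 9.8% | 6.2% | 5.1% |
| 0.4 SD | 22.8% | 19.9% | 9.5% | 6.3% |

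At N=150 to 300, coverage of the 95% interval is therefore 100 − 22.8 = 77% at worst and 100 − 9.8 = 90% at best.

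Variations on the same setting:
- A logistic outcome (log odds ratio 0.25 per SD, 1,500 replicates) gave similar rates: 10.7%, 8.8%, 7.5% at N=150, 300, 600 with 0.2 SD, and 22.7%, 20.5%, 11.6% with 0.4 SD.
- Univariable screening at 0.05 was milder: about 7 to 11% at N=150 to 300.
- All confounders forced in: 4.6 to 5.2% (linear) and 4.1 to 5.9% (logistic).
- No confounding at all: 5.2%, so selection alone caused no inflation.

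**Step 4: what clinical rationale can save.** A second setting has 30 candidates of which 8 are true confounders, 0.35 SD imbalance, 0.12 SD effect, all biases in one direction, one third of patients in the discontinued cohort, and 600 replicates:

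| Rule | n=200 | n=300 | n=600 |
|---|---|---|---|
| Elimination at 0.05, nothing protected | 17.8% | 15.7% | 8.7% |
| 4 of 8 confounders kept on clinical grounds | 8.5% | 8.2% | 6.5% |
| 6 of 8 kept | 5.7% | 7.3% | 6.8% |
| Elimination at 0.20, nothing protected | 9.8% | 7.7% | 5.7% |

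Monte Carlo standard error: √(0.178 × 0.822 / 600) = 1.6 points for the largest entry and √(0.085 × 0.915 / 600) = 1.1 points for one near 8.5%, so small differences between cells mean little. With confounders pulling in mixed directions, unprotected elimination gave about 11%, 12% and 9%. With the full confounder set forced in, the rate was about 4 to 6%.

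**The case against.** The strongest reply is that the rule joins clinical rationale to significance. It names no elimination procedure and nowhere says that a non-significant covariate must leave. It can be read as keeping clinically chosen variables and applying p-values only to the rest. This stands as a limit on the claim: confounders can be dropped, and the highest rates above apply only if clinical judgement rescues nothing. It does not clear the rule, because the text does not say whether one criterion suffices or both are needed, and it protects no variable by name.

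Three stronger readings are tempting, and the documents do not support them.
- A reader might infer that the reported intervals will certainly cover less than 95%. That depends on N, threshold and strength of confounding, none of which is stated, and the problem nearly vanishes at N=1000 in most settings tried.
- A reader might infer that these models are the study's only control of confounding. Section 8.10.1 also names effect decomposition, section 8.10 repeats the objectives by insurance type and prior biologic experience, and the effectiveness model lists demographics without a significance condition. These are partial mitigations: decomposition is offered only as a possible solution and has no covariate list of its own.
- A reader might treat different adjustment sets for different outcomes as an error. Cost and a composite effectiveness flag can have different determinants, so a different set is acceptable if fixed in advance.

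It is also fair to note that CIRAS already contains age and sex, and that effectiveness criteria 4 and 5 in 8.6.4 are defined relative to baseline NB-DMARD and glucocorticoid use. Both deserve thought when the set is written. Neither is a reason to choose by p-value.

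**Conclusion.** The point holds in conditional form. Section 8.10.2 lets significance help decide which confounders enter a confounding-control model and guarantees none of them, in a study that the plan itself expects to be small and imbalanced. The adjusted secondary cost and effectiveness comparisons can therefore keep bias that the data could have removed, with intervals that are too optimistic.

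The direction is firm; the size rests on assumption. With eight modest confounders and elimination at 0.05, the cohort false-positive rate is roughly 15 to 18% at n=200 to 300 when nothing is kept clinically. It is roughly 6 to 10% when half or more are kept or the threshold is 0.20, and near 5% when all are forced in. The harm comes from residual confounding, so it fades as N grows and is absent where there is no confounding. This is a cheap improvement, not a flaw that invalidates the study.

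**What to change.** In 8.10.2, remove statistical significance as an entry criterion for confounders. Pre-specify a confounder set from clinical knowledge, restricted to pre-index measures, and keep it in the model whatever the p-values. A workable set from variables the plan already defines or records: age, sex, insurance type, index year, number of prior biologics, pre-index MTX and other NB-DMARD use, CIRAS, Quan-Charlson score, and baseline oral corticosteroid, opioid and NSAID use. State that the post-index measures in 8.6.2 are not eligible as covariates. The set may differ between cost and effectiveness if the SAP says so before results are seen.

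Where patients or events are too few for the full set, enter it through a propensity score used as a covariate or weight, or use penalised regression that leaves the cohort term unpenalised. Neither requires discarding unmatched patients, which is the loss that 8.10.6 fears from matching.

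The cost is SAP wording and no new data. The statistical downside is somewhat wider intervals where a retained covariate proves unimportant; how much wider cannot be stated without N and event counts.

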### **8.10.3. Cost Data**

Because health care costs are often skewed, estimated cost measures will be modeled using Manning and Mullahy's formulation. This method avoids potential difficulties introduced by transformation and retransformation of the dependent variable. Coefficients from a generalized linear model (GLM) are estimated cost ratios. Cost ratios, 95 percent confidence intervals, and p-values will be presented for each categorical covariate included in the model. For ease of interpretation and comparison with the bivariate results, the average cost will be predicted for each cohort and may also be predicted for pre-determined levels of other patient characteristics (eg, combination vs. monotherapy, gender).

If a significant number of patients have zero values for costs (eg, more than 5% in one of tofacitinb+MTX patients who withdraw MTX or continue MTX groups), estimated cost measures will be compared using Blough et al.'s formulation of the traditional two-part model (ie, one equation estimating the probability of any cost and a GLM with a gamma distribution and log link estimating the level of cost). This method avoids potential difficulties introduced by transformation and retransformation of the dependent variable.

Odds ratios, 95 percent confidence intervals, and p-values will be presented for each categorical covariate included in the logistic model estimating the probability of non-zero costs, if any. Cost ratios, 95 percent confidence intervals, and p-values will be presented for each categorical covariate included in the GLM model estimating the level on costs. For continuous covariables of both models, estimates and their 95 percent confidence intervals, and p-values will be presented.

### **8.10.4. Dichotomous Data**

For binary variables, the probability of achievement (eg, being effectively treated at one year) will be modeled using logistic regression. For ease of interpretation, the results of logistic regression will be presented as odds ratios, 95 percent confidence intervals, and p-values for each categorical covariate included in the model, and for continuous covariables, estimates and their 95 percent confidence intervals, and p-values will be presented.

---

 Manning WG. The logged dependent variable, heteroskedasticity, and the retransformation problem. *J Health Econ.* 1998;17(3):283-295.

### **8.10.5. Other Continuous Data**

For continuous variables, mean values will be modeled using a normal model. The results will be presented as mean differences, 95 percent confidence intervals, and p-values for each categorical covariate included in the model, and for continuous covariables, estimates and their 95 percent confidence intervals, and p-values will be presented.

### **8.10.6. Decomposition**

Given that the sample size for this study will be relatively small and the comparator populations will be noticeably different, implementing propensity score matching may reduce the available sample below what is needed for a meaningful study. One possible solution would be to implement a method known as decomposition [Blinder (1973), Oaxaca (1973)] Decomposition splits out the treatment effect into two parts, the effect of the actual treatment and the effect of the other differences between the treatment groups. Presumably, if the treatment groups were randomly assigned, then the effect of the treatment would be the entire effect and the effect of all other differences would be negligible. However, since biologic treatment choice is not randomly assigned, the decomposition method would determine how much of the treatment effect is due to the medication and how much is due to the difference in characteristics between the two tofacitinib cohorts (tofacitinib+MTX patients who withdraw MTX or continue MTX).

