#### **8.10.1. Descriptive Analysis**

All study variables, including pre- and post-index measures, will initially be analyzed descriptively. In general, numbers and percents will be provided for dichotomous and polytomous variables, while means, medians, and standard deviations will be provided for continuous variables. Missing or unavailable data will not be imputed.

Results will be stratified by treatment cohort, bivariate comparisons of pre- and post-index measures will be provided, and appropriate tests (eg, t-test, Mann Whitney-U test, chi-square test) will be used based on the distribution of the measure. The analysis that is performed (ie, the methods that are used and the patients who are included) will be specific the objective being examined. Descriptive techniques will be implemented for each objective.

Multivariable techniques (including effect decomposition) will be used when comparing outcomes and controlling for differences in patient characteristics between study cohorts.

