### **8.12. Limitations of the Research Methods**

#### **8.12.1. Claims**

Limitations that are general to claims database analyses and specific to this study should be noted. First, diagnosis of autoimmune conditions will be identified using ICD-10-CM diagnosis codes, which are subject to potential miscoding. Second, the baseline period for this study will be 12 months long. Therefore, patients treated with a biologic in the baseline can be considered to be continuing users of biologic therapy; however, patients with no biologic use in the baseline may have just been off therapy for the 12 months prior. Lastly, this study will include an examination of medication effectiveness at 1 year among all biologic users. Effectiveness will be measured using a validated algorithm; however, the algorithm was not validated for all medications being included. Specifically, tofacitinib was approved for treatment of RA after the algorithm was developed. This study will include consultation with physicians to determine if the algorithm is valid for all study medications or if modifications need to be implemented.

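### Section 8.10.6 credits the unexplained part of the decomposition to the medication, although that part also contains unmeasured differences that affect the outcome and that the covariates do not capture

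*Combined protocol and SAP*

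**What the plan says.** Section 8.10.6 sets propensity score matching aside because the sample may become too small, and notes that "the comparator populations will be noticeably different". It then offers Blinder-Oaxaca decomposition, described as giving two parts: "the effect of the actual treatment and the effect of the other differences between the treatment groups". It concedes that allocation is not random ("since biologic treatment choice is not randomly assigned") and concludes that "the decomposition method would determine how much of the treatment effect is due to the medication", the remainder being due to differences in characteristics between the two tofacitinib cohorts.

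On whether the method will be used, 8.10.6 is tentative ("One possible solution would be to implement a method known as decomposition"), while 8.10.1 is firm: "Multivariable techniques (including effect decomposition) will be used when comparing outcomes and controlling for differences in patient characteristics between study cohorts".

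Section 8.10.2 draws the covariates from 8.6.1 and 8.6.2, plus any variables identified during the study. Section 8.12.1 opens with "Limitations that are general to claims database analyses and specific to this study should be noted" and then lists diagnosis miscoding, the 12-month baseline and the validity of the effectiveness algorithm. It does not list unmeasured confounding, and no sensitivity analysis for it is planned.

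**The concern.** The two-part description leaves no place for differences that the claims data do not record. In a Blinder-Oaxaca split, the explained part covers only the covariates in the model. Everything else that differs between the cohorts and affects the outcome falls into the other part, which 8.10.6 treats as the effect of the medication.

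This matters for these cohorts in particular. All patients start tofacitinib with oral MTX, and what separates them is a gap of more than 60 days in MTX fills during the 12 months after index (8.3). Good disease control, intolerance and general non-adherence are all plausible reasons for such a gap, and each could affect costs or effectiveness. No variable records the reason. Because the outcomes are measured over the same 12 months (8.5), the course on tofacitinib may itself lead to MTX being stopped, and that too would enter the part labelled as medication.

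The report could therefore state that a given share of a cost or effectiveness difference is due to the medication when withdrawing MTX has no effect. The direction cannot be fixed in advance: stopping because the patient is well and stopping because of intolerance would push the result opposite ways.

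**Working it through.** The plan gives no sample size, effect size or decomposition result, so there is no figure of its own to reproduce. The algebra comes first, then an illustration on assumed inputs.

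**Algebra.** Let cohort 1 withdraw MTX and cohort 0 persist. With a separate linear fit in each cohort,

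mean(Y1) − mean(Y0) = [mean(X1) − mean(X0)]·β0 + mean(X1)·(β1 − β0).

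The first term is the explained part and the second the unexplained part. Suppose Y also depends on an unmeasured factor U with coefficient b, that U differs between cohorts by d, and that the true effect of withdrawal is τ. If U is independent of X within cohorts, the expected unexplained part is

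τ + b·d.

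If U has correlation ρ with a single measured covariate whose cohort shift is dx (both with unit SD), it is

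τ + b·(d − ρ·dx).

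**Check of the algebra.** τ = 0, residual SD 1, one measured covariate with coefficient 0.3 and dx = 0.3, 4,000 replicates:

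| d | b | b·d | Mean unexplained part, 200+300 patients | Rejection at 100+150 / 200+300 / 400+600 |
|---|---|---|---|---|
| 0 | 0.4 | 0 | −0.001 | 5.2 / 5.0 / 4.8% |
| 0.3 | 0.3 | 0.09 | 0.089 | 9.7 / 15.5 / 26.7% |
| 0.5 | 0.4 | 0.20 | 0.202 | 29.6 / 51.9 / 79.5% |
| 0.5 | 0.6 | 0.30 | 0.298 | 49.3 / 78.4 / 97.6% |

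With ρ = 0.5, d = 0.5, b = 0.4 and dx = 0.3, the formula gives 0.4 × (0.5 − 0.5 × 0.3) = 0.14. The simulation gives 0.142, and rejection at 200+300 falls from 51.9% to 30.2%. If X captures U fully, the bias is 0 and rejection is 5.1%.

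**Illustration closer to the plan.** Three measured covariates X1-X3 and U, all standard normal; logit P(withdraw) = −0.7 + 0.4·X1 + 0.3·X2 + ln(OR)·U, so about one third withdraw; Y = 0.3·X1 + 0.2·X2 + b·U + N(0,1), with no cohort effect. The test is two-sided at 5%, with 2,000 data sets per cell. Every value here is an assumption.

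| OR per SD of U | b (SD) | N=200 | N=400 | N=800 |
|---|---|---|---|---|
| 1 | – | 5.1% | 4.4% | 4.1% |
| 1.5 | 0.3 | 11.0% | 17.3% | 29.0% |
| 1.5 | 0.5 | 19.6% | 37.5% | 63.6% |
| 2 | 0.3 | 20.3% | 38.9% | 65.5% |
| 2 | 0.5 | 42.8% | 75.6% | 96.6% |

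Repeat runs gave up to 33% in the second row at N=800 and 95-96% in the last row at N=800; hence the ranges 11-33% and 43-97%.

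**Share of the difference.** The mean unexplained part divided by the mean raw difference is about 0 with no unmeasured confounding and about 42-69% across the confounded rows. The median absolute share should not be used: with no unmeasured confounding it is already 56%, 41% and 30% at N = 200, 400 and 800, through sampling noise in a ratio.

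**Proxies.** With U correlated 0.5 with X1, rejection at N=400 falls from 75.6% to 47.5% (OR 2, b 0.5) and from 17.3% to 11.8% (OR 1.5, b 0.3).

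**The case against.** - **Every adjustment method has this limit.** This is correct. In the same simulated data at N=400, ordinary covariate-adjusted regression rejects in 17.8% and 76.4% of runs, against 17.3% and 75.6% for the decomposition. A reader might infer that decomposition is worse than the GLM or logistic models; nothing here supports that. The difference lies in the wording. Sections 8.10.3 and 8.10.4 promise cost ratios and odds ratios, whereas 8.10.6 says what share is due to the medication.
- **The plan does measure severity and intolerance in part.** This is also correct. Section 8.6.2 lists CIRAS, corticosteroid dose, opioid and NSAID use, rheumatologist visits, prior biologics and NB-DMARDs, disease duration, and liver and kidney disease flags, and 8.10.2 allows more. It would be wrong to infer that severity enters through a single index, or that the residual holds every unmeasured reason for stopping. Only reasons that affect the outcome and escape these proxies matter. But these are baseline claims measures, and they may capture only partly why MTX stopped after index.
- **The plan states no null hypothesis or test for the decomposition.** This is true: the objectives are to compare and explore. The 5% test and the normal outcome were supplied for the illustration, while the outcomes named in 8.10.2 are costs and a yes/no effectiveness measure. The rejection rates show how the problem behaves; they do not predict this study's results.
- **Decomposition is optional.** This holds only for 8.10.6 read alone, since 8.10.1 says it will be used.

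**Conclusion.** The point holds as a fault of interpretation. Section 8.10.6 claims a property that the decomposition lacks, and neither it nor 8.12.1 states the assumption of no unmeasured confounding that the claim would need. For a linear outcome, the unexplained part equals any effect of MTX withdrawal plus b times the cohort shift in the unmeasured factor that the covariates leave uncaptured.

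The size cannot be read from the documents. On the assumed inputs, with the unmeasured factor independent of the covariates, false rejection is 11-33% for the moderate factor and 43-97% for the stronger one over N=200-800, against about 5% without confounding. For a given bias it rises with sample size; it falls as the covariates capture more of the factor.

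A reader might go further and conclude that the report will announce an effect where there is none. The documents do not support that: no reporting text commits to such a statement, and the bias could be small or run either way. What they support is that a difference can be misattributed, and that nothing in the plan guards against it.

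**What to change.** In Section 8.10.6, replace the attribution with:

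> The decomposition separates the observed cohort difference into a part explained by the measured baseline characteristics and a part not explained by them. The unexplained part includes any effect of MTX withdrawal and all unmeasured differences and will not be reported as the effect of the medication.

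Report the unexplained part with a bootstrap 95% confidence interval and a simple bias grid: the cohort shift of an unmeasured factor multiplied by its effect on the outcome, on the outcome's own scale. Readers can then see how strong such a factor would have to be to account for the result.

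Add to Section 8.12 that the reasons for stopping MTX are not recorded and may affect the outcomes, and that this limitation applies equally to the GLM and logistic models.

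The cost is a change of wording and a little extra analysis, with no new data. The downside is a weaker conclusion.
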